11.0 Definition of an Adverse Event

An adverse event or experience is defined as any symptom, sign, illness, or untoward experience (including a clinically significant laboratory finding classified as grade ≥ 3 by the National Cancer Institute's Common Terminology Criteria for Adverse Events [CTCAE]; appendix C) that develops or worsens during the course of the study, whether or not the event is considered related to study drug. Any adverse event should be recorded only after the first dose of study drug is taken. Serious adverse events are recorded from the time the informed consent form is signed.

Where a diagnosis is possible, it is preferable to record it rather than a series of terms relating to the diagnosis.

An abnormality identified during a medical test (e.g., laboratory parameter, vital sign, ECG data, physical exam) should be defined as an AE only if the abnormality meets one of the following criteria:

- Induces clinical signs or symptoms.
- Requires active intervention.
- Requires interruption or discontinuation of study medication.
- The abnormality or investigational value is clinically significant in the opinion of the investigator.

All adverse events, whether or not related to the study drug, must be fully and completely documented.

Adverse events are detected in two ways:

- Clinical: symptoms reported by the patient or signs detected on examination;
- Ancillary Tests: clinically significant abnormalities of vital signs, ECG, laboratory tests, and other diagnostic procedures.

An adverse event **does not** include:

- Medical or surgical procedures (e.g., surgery, endoscopy, tooth extraction, transfusion); however, the condition that leads to the procedure is an adverse event;
- Pre-existing diseases or conditions present or detected prior to the start of study drug administration that does not worsen;
- Situations where an untoward medical event has not occurred (e.g., hospitalization for elective surgery, social and/or convenience admissions);
- Overdose of either study drug or concomitant medication without any signs/symptoms

Relationship to Study Drug: The reasonable possibility of an adverse event's relationship to study drug is to be assessed with careful medical consideration at the time of evaluation of the adverse event. The PI's opinion may be sought in those cases in which the Investigator is unable to make an independent judgment. The following definitions are to be used:

Descriptor	Definition
Unrelated	Adverse event is clearly not related to the investigational drug (s)
Unlikely	Adverse event is doubtfully related to the investigational drug (s)

Page 38 of 82

Possible	Adverse event is may be related to the investigational drug (s)
Probable	Adverse event is likely related to the investigational drug (s)
Definite	Adverse event is clearly related to the investigational drug (s)

The following criteria will be used as guidelines for determining the attribution of an adverse event to the study drug:

Unrelated	There is no possible relationship to the study drug. The temporal relationship between drug exposure and the adverse event onset/course is unreasonable or incompatible, or a causal relationship to study drug is implausible.
Unlikely	The study drug is believed to be not reasonably related to the adverse event, although a causal relationship cannot be ruled out. While the temporal relationship between drug exposure and the adverse event onset/course does not preclude causality, there is a clear alternate cause that is more likely to have caused the adverse event than the study drug.
Possible	The causal relationship to the study drug is uncertain. The temporal relationship between drug exposure and the adverse event onset/course is reasonable or unknown, dechallenge or rechallenge information is either unknown or equivocal, and while other potential causes may not exist, a causal relationship to the study drug does not appear probable.
Probable	There is a high degree of certainty for a causal relationship between the study drug and the adverse event. The temporal relationship between drug exposure and the adverse event onset/course is reasonable, there is a clinically compatible response to dechallenge, other causes have been eliminated, and the event must be definitive pharmacologically or phenomenologically, using a satisfactory rechallenge procedure if necessary.
Definite	Causal relationship is certain. The temporal relationship between drug exposure and the adverse event onset/course is reasonable, there is a clinically compatible response to dechallenge, other causes have been eliminated, and the event must be definitive pharmacologically or phenomenologically, using a satisfactory rechallenge procedure if necessary.

procedure if necessary.

In the event that a patient is withdrawn from the study because of an adverse event, it must be recorded. Adverse events will be monitored until resolution or until the event has stabilized and/or reached a new baseline. If an adverse event remains unresolved at the conclusion of the study, a clinical assessment will be made by the investigator to determine whether continued follow-up of the adverse event is warranted.

The investigator must record all directly observed adverse events and all spontaneously reported adverse events. At each visit, the investigator will ask the patient a non-specific question (e.g., "Have you noticed anything different since your last visit?") to assess whether any adverse event has been experienced since the last report or visit. Adverse events will be identified and documented. The severity and the relationship to the study drug will be determined and reported.

Note that any intermittent or as needed use of any medication (and specifically any newly prescribed medication) during the course of a study may indicate the occurrence of an adverse event that may need to be recorded.

Serious adverse events will be collected and reported from the time the patient signs the informed consent form until the Safety Follow-Up visit. Non-serious adverse events will be collected from the time of first study drug dosing until the Safety Follow-Up visit.

11.1 Adverse Events - Severity Rating

Severity describes the intensity of a specific event (as in mild, moderate, or severe chest pain); the event itself, however, may be of relatively minor medical significance (such as severe headache). This is not the same as "serious," which is based on patient/event outcome or action criteria. The severity of an adverse event will be graded following the CTCAE v4.0 (appendix C).

11.2 Disease Progression as an Adverse Event

It is anticipated that a proportion of patients will experience disease progression. **Disease progression per se should NOT be reported as an adverse event.** If there are separate identifiable clinical sequelae that result from disease progression, these sequelae are reportable as adverse events.

11.3 Serious Adverse Events and Unexpected Adverse Events - Definitions

A Serious Adverse Event or reaction is any untoward medical occurrence at any dose that:

- Results in death;
- Is life threatening (i.e., the patient was at immediate risk of death at the time of the event). "Life-threatening" does not include an event that hypothetically might have caused death if it were more severe. For example, drug-induced hepatitis that resolved without evidence of hepatic failure would not be considered life-threatening even though drug-induced hepatitis can be fatal;

- Requires inpatient hospitalization or prolongation of existing hospitalization;
- Results in persistent or significant disability/incapacity (i.e., a substantial disruption of the patient's ability to carry out normal life functions);
- Is a congenital anomaly/birth defect.

In addition, medical and scientific judgment should be exercised in deciding whether other situations should be considered a serious adverse event (i.e., important medical events that may not be immediately life-threatening or result in death, but may jeopardize the patient or may require medical or surgical intervention to prevent one of the other outcomes listed in the definition above). Examples of such medical events include (but are not limited to): allergic bronchospasm requiring intensive treatment in an emergency room or at home, blood dyscrasias or convulsions that do not result in in-patient hospitalization, or the development of drug dependency or drug abuse. In this study, a documented seizure should be reported as a medically important serious adverse event.

11.4 Serious Adverse Events - Reporting

The study team should report serious adverse events (SAEs) to the DSMC using the SAE report form on University of Rochester's OnCore platform. If the SAE(s) is related to study medication and is unexpected (SUSARs), the SAE(s) should be reported to the DSMC and RSRB within 5 days and to the FDA within 7 days. If the SAE(s) is unrelated to study medication and/or expected, the SAE(s) report needs to be completed, including all follow up information, prior to the next scheduled review of the study by DSMC. To report SAEs, the Investigator will also submit a SAE report to Astellas by either e-mail or fax, within the same timeframe as required by the DSMC.

For participating sites that do not have access to the University of Rochester's OnCore platform, they can use the MedWatch Form 3500 to report non-SUSAR SAE(s) and the MedWatch Form 3500A to report SUSAR(s) to the sponsor-investigator. Then, the sponsor-investigator team will enter the SAEs/SUSARs into the SAE report form on the University of Rochester's OnCore platform using the same timeline as detailed above.

For all SUSARs, the MedWatch 3500A form should be completed and faxed to Astellas and FDA by either e-mail or fax, within 7 days. If submission of SUSARs to FDA or Astellas or Medivation is not possible within 7 days, the Investigator's local drug safety contact (e.g., DSMC, IRB, etc.) should be informed by phone.

The SUSAR documentation, including the Medwatch 3500A Form and available source records should be emailed or faxed to:

Astellas Pharma Global Development – United States
Email: [contact]
[contact]

The following minimum information is required for the initial report:

Study number/IIT regulatory identifier

Subject number, sex and age

The date of report

The start date of the event

As much information as is known about the event at the time

Suspected causal relationship to the study drug

Whether the event is known to occur in relation to the study drug (i.e., expectedness)

Follow-up information for the event should be sent within promptly (within 7 days) as necessary.

It is the responsibility of the investigator to report serious adverse events to their local IRB/IECs according to their policies.

All serious adverse events should be recorded once the informed consent form is signed and must be reported within the timeframe as discussed above by facsimile to the person listed below

Name: [name]

SAE [contact]

Email: [contact]

[contact]

Follow up reports should include the same information as the initial report with any updates or corrections needed. In addition, they should include the details of study drug administration, and as many details of the serious adverse event as are known, including the date of onset, the intensity, the treatment, and the relationship to study drug. SAE reports must include sufficient detail so that the DSMC can determine the CTCAE term, severity, toxicity grade, expectedness, relatedness, treatment required, and a follow up report documenting resolution and whether there are sequelae. If the patient died, the report should include the cause of death and whether or not the death was related to study drug, as well as the autopsy findings if available.

Do not delay reporting a suspected serious adverse event in order to obtain additional information. Any additional information should be reported in a follow-up to the initial report.

All serious adverse events will be followed until resolution or until the event has stabilized and/or reached a new baseline. All serious adverse events continuing at the completion of the study must be followed to determine outcome. All serious adverse events occurring between the times the patient signs the informed consent and 30 days after the patient's last dose of study drug or prior to the initiation of another systemic antineoplastic therapy, whichever occurs first, must be recorded, reported, and followed up by the investigator using the procedure described above.

11.5 Procedure in Case of Pregnancy

The effect of enzalutamide in pregnant and lactating women is not known, and the exposure of a fetus or nursing infant is considered a potential risk. Enzalutamide can cause fetal harm when administered to a pregnant woman based on its mechanism of action. Subjects receiving enzalutamide are advised to use 2 acceptable methods of birth control (one of which must include a condom as a barrier method of contraception) starting at the time of screening for an enzalutamide study and continuing throughout the course of treatment and for at least three months after enzalutamide is discontinued.

Dutasteride is contraindicated for use in women of childbearing potential and during pregnancy. Dutasteride prevents conversion of testosterone to DHT, a hormone necessary for normal development of male genitalia. In animal reproduction and developmental toxicity studies, dutasteride inhibited normal development of external genitalia in male fetuses. Therefore, dutasteride may cause fetal harm when administered to a pregnant woman. If this drug is used during pregnancy or if the patient becomes pregnant while taking it, the patient should be apprised of the potential hazard to the fetus

If during the conduct of the clinical trial, a male subject impregnates his partner, the subject should report the pregnancy to the Investigator. The Investigator should report the pregnancy to the Sponsor as an SAE within 24 hours of awareness of the event. The expected date of delivery or expected date of the end of the pregnancy, last menstruation, estimated fertility date, pregnancy result and neonatal data etc., should be included in this information.

The Investigator should report the outcome of the pregnancy (independent of outcome, eg. full term delivery, pre-term delivery, spontaneous abortion, induced abortion, stillbirth, death of newborn, congenital anomaly [including anomaly in a miscarried fetus, etc] in accordance with the same reporting procedure as for SAEs. The date of outcome of the pregnancy, gestational age, date of birth and neonatal data etc., should be included in this information.

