3.1.2 Pharmacology

Mechanism of action: Enzalutamide is an androgen receptor inhibitor that acts on multiple steps in the androgen receptor signaling pathway. Enzalutamide has been shown to competitively inhibit androgen binding to androgen receptors and inhibit androgen receptor nuclear translocation and interaction with DNA. A major metabolite, N-desmethyl enzalutamide, exhibited similar *in vitro* activity to enzalutamide.

Enzalutamide decreased proliferation and induced cell death of prostate cancer cells *in vitro* and decreased tumor volume in a mouse prostate cancer xenograft model.

Pharmacokinetics: Data indicate the pharmacokinetics of enzalutamide and its major active metabolite (N-desmethyl enzalutamide) evaluated in patients with metastatic castration-resistant prostate cancer and healthy male volunteers note a linear two-compartment model with first-order absorption. The median time to reach maximum plasma enzalutamide concentrations (Cmax) is 1 hour (range 0.5 to 3 hours).With the daily dosing regimen, enzalutamide steady state is achieved by Day 28, and enzalutamide accumulates approximately 8.3-fold relative to a single dose. Daily fluctuations in enzalutamide plasma concentrations are low (mean peak-to-trough ratio of 1.25). At steady state, enzalutamide showed approximately dose proportional pharmacokinetics over the daily dose range of 30 to 360 mg. A single 160 mg oral dose was administered to healthy volunteers with a high-fat meal or in the fasted condition. A high-fat meal did not alter the AUC to enzalutamide or N-desmethyl enzalutamide.

Enzalutamide is 97% to 98% bound to plasma proteins, primarily albumin. N-desmethyl enzalutamide (active metabolite) is also 95% bound to plasma proteins. Following single

oral administration of 14C-enzalutamide, its metabolites were detected up to 77 days post dose. *In vitro*, human CYP2C8 and CYP3A4 are responsible for the metabolism of enzalutamide. Based on *in vivo* and *in vitro* data, CYP2C8 is primarily responsible for the formation of the active metabolite (N-desmethyl enzalutamide). Enzalutamide is primarily eliminated by hepatic metabolism. The mean terminal half-life (t_{1/2}) for enzalutamide in patients after a single oral dose is 5.8 days (range 2.8 to 10.2 days).

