Dutasteride and its metabolites were excreted mainly in feces. As a percent of dose, there was approximately 5% unchanged dutasteride (~1% to ~15%) and 40% as dutasteride-related metabolites (~2% to ~90%). Only trace amounts of unchanged dutasteride were found in urine (<1%). Following daily dosing, dutasteride serum concentrations achieve 65% of steady-state concentration after 1 month and approximately 90% after 3 months. Due to the long half-life of dutasteride, serum concentrations remain detectable (greater than 0.1 ng/mL) for up to 4 to 6 months after discontinuation of treatment. The terminal elimination half-life of dutasteride is approximately 5 weeks at steady state.

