3.2.5 Pregnancy

Pregnancy Category X. Dutasteride is contraindicated for use in women of childbearing potential and during pregnancy. Sexually active men with partners in child bearing age group are recommended contraceptive use when taking this medication.

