3.4 Blood Donation

Men being treated with study drugs should not donate blood until at least 6 months have passed following their last dose. The purpose of this deferred period is to prevent administration of study drug to a pregnant female transfusion recipient, for which this drug is not safe.

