7.1 Treatment

All patients will receive either a combination of enzalutamide 160 mg oral daily and dutasteride 0.5 mg oral daily or enzalutamide 160 mg oral daily and finasteride 5 mg oral daily until disease progression or other reasons for removal from treatment protocol. (see section 7.4). The type of 5-AR inhibitor used for each patient will depend on insurance approval. Dutasteride will be the 5AR-Inhibitor of choice given its slightly better efficacy. If for any reason dutasteride cannot be obtained, finasteride would be administered.

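### For men on dutasteride, the minimum contraception period in 11.5 can end 1 to 3 months before the drug is undetectable by the protocol's own figure

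*Combined protocol and SAP*

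**What the plan says.** All references are to the combined protocol and SAP.

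- **Contraception, 11.5.** Men receiving enzalutamide are advised to use two methods, one of them a condom, from screening and "continuing throughout the course of treatment and for at least three months after enzalutamide is discontinued". Section 7.1 gives enzalutamide to every patient, so this advice reaches everyone.
- **Dutasteride, 11.5.** The next paragraph describes impaired genital development in male fetuses in animal studies and concludes: "Therefore, dutasteride may cause fetal harm when administered to a pregnant woman". It gives no period for precautions.
- **Dutasteride, 3.2.5.** The drug is labelled Pregnancy Category X. The advice for men covers treatment only: "Sexually active men with partners in child bearing age group are recommended contraceptive use when taking this medication".
- **Persistence, 3.2.2.** After dutasteride is stopped, "serum concentrations remain detectable (greater than 0.1 ng/mL) for up to 4 to 6 months after discontinuation of treatment". Also: "The terminal elimination half-life of dutasteride is approximately 5 weeks at steady state".
- **Blood donation, 3.4.** Men on study drugs "should not donate blood until at least 6 months have passed following their last dose". The stated purpose is to keep study drug from a pregnant transfusion recipient.
- **Choice of drug, 7.1.** "Dutasteride will be the 5AR-Inhibitor of choice given its slightly better efficacy". Finasteride is the fallback.

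**The concern.** The only post-dose contraception period in the protocol is counted from the last dose of enzalutamide. Three months suits that drug, whose mean half-life is 5.8 days with a stated range of 2.8 to 10.2 days (3.1.2). It does not suit a companion drug with a half-life of about 5 weeks. The protocol itself says dutasteride may harm a fetus, gives its persistence in months, and uses 6 months when the route of exposure is donated blood.

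A man on the preferred regimen could therefore comply fully with 11.5 and stop precautions while dutasteride is still detectable and while he is still barred from giving blood. What is at stake is the protection of a partner and a pregnancy. The efficacy and safety analyses are not involved.

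**Working it through.** **Inputs**

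| Quantity | Value | Source |
|---|---|---|
| Minimum contraception after enzalutamide | 3 months | 11.5 |
| Post-dose contraception for dutasteride | none stated | 11.5, 3.2.5 |
| Dutasteride detectable (above 0.1 ng/mL) after stopping | up to 4 to 6 months | 3.2.2 |
| Dutasteride half-life | about 5 weeks = 35 days | 3.2.2 |
| Enzalutamide half-life, single dose | mean 5.8 days, longest 10.2 days | 3.1.2 |
| Blood-donation deferral | 6 months | 3.4 |

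One month is taken as 30.44 days, so 3 months = 91.3 days and 6 months = 182.6 days.

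**Step 1: gap when both drugs stop together.** This is the default, since both are given until progression or another reason for removal (7.1, 7.4).

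- Against detectability: 4 − 3 = 1 month to 6 − 3 = 3 months.
- Against the blood-donation deferral: 6 − 3 = 3 months.

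**Step 2: gap when dutasteride stops first.** Section 12 allows the 5-AR inhibitor to be held permanently for its own toxicity. If dutasteride stops k months before enzalutamide, the gap against detectability runs from max(0, 1 − k) to max(0, 3 − k). It is zero throughout once k is 3 or more.

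**Step 3: fraction remaining.** First-order decline is assumed: fraction = 2^(−t / half-life).

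- Dutasteride at 3 months: 91.3/35 = 2.6 half-lives; 2^(−91.3/35) = 0.164, about 16%.
- Dutasteride at 6 months: 2^(−182.6/35) = 0.027, about 2.7%.
- Enzalutamide at 3 months, mean half-life: 2^(−91.3/5.8) = 0.000018, about 0.002%.
- Enzalutamide at 3 months, longest stated half-life: 2^(−91.3/10.2) = 0.0020, about 0.2%.

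The enzalutamide figures are for the parent drug only. Section 3.1.2 also reports metabolites detected up to 77 days after a single dose, which is still shorter than 91.3 days.

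**Step 4: consistency of the two dutasteride figures.** The 4 to 6 months cannot be rebuilt from the half-life, because no steady-state concentration is given. Working back from the detection limit instead:

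- Limit reached at 4 months: level at 3 months = 0.1 × 2^(30.4/35) = 0.18 ng/mL.
- Limit reached at 6 months: level at 3 months = 0.1 × 2^(91.3/35) = 0.61 ng/mL.

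The implied level when the 11.5 minimum ends is 1.8 to 6.1 times the limit. This restates the 4 to 6 months as concentrations. It is not independent evidence.

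**Step 5: finasteride.** Its stated half-life is about 6 hours, or 8 hours at age 70 and over (3.3.2). The three-month rule is ample for it.

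**The case against.** The strongest reply is that the three-month sentence concerns enzalutamide and never claims to cover dutasteride, so the fault is only a missing duration. It is also a minimum set against an upper range. That makes 1 to 3 months the largest gap, not a certain one. This stands as a limit on the size, but the minimum is the only figure a site or patient is given, and a fetal precaution should cover the upper range.

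Second, detectable does not mean harmful. The documents give no semen level, no estimate of sexual transfer and no harmful concentration, and the 6 months in 3.4 concerns transfusion. The two periods need not be equal, so harm cannot be claimed. Still, 11.5 asks for a condom and 3.2.5 recommends contraception, so the protocol already treats partner exposure as worth preventing. It sets no end date suited to dutasteride.

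Third, the men are 65 or older, the earlier retrospective cohort treated with an antiandrogen plus 5-AR inhibitor had a median age of 86 (1.2), and 3.1.3 says enzalutamide may impair male fertility. The number affected could be zero. That stands and keeps the practical weight low. Section 11.5 nevertheless contains a procedure for partner pregnancy, so the event was foreseen.

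Finally, the consent form, the investigator's brochures or the retail pharmacy may supply the advice. That cannot be checked here. It would not remove the inconsistency within the protocol.

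**Conclusion.** The concern holds. For men on dutasteride, the minimum contraception period falls short of the stated detectability by 1 to 3 months and of the blood-donation deferral by 3 months, and no contraception period after dutasteride is given.

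These figures assume that both drugs stop together and that the man observes only the minimum. The percentages and concentrations also assume first-order decline at the stated half-lives. The number of men on dutasteride with a partner of childbearing age is not given. It is assumed to be small, out of about 40 enrolled. The text should be corrected as a safety precaution; sample size, power and analysis are unaffected.

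**What to change.** In 11.5 and 3.2.5, state that men who received dutasteride continue contraception until at least 6 months after their last dutasteride dose and at least 3 months after their last enzalutamide dose, whichever is later. This closes the gap at the upper end of the range in 3.2.2, agrees with 3.4, and handles early stopping of dutasteride. Men who received only finasteride keep the three-month enzalutamide rule.

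The cost is one sentence in each section and up to 3 more months of precaution for the few men concerned. Any patient-facing instructions should be checked for the same wording.
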